## A retrospective review of patient notes to establish the usual care of Ovarian Hyper-Stimulation Syndrome and the feasibility of the full STOP-OHSS Randomised Controlled Trials: Protocol v2, 19/09/20

## 1. Background

## What is Ovarian Hyper-Stimulation Syndrome (OHSS)

Ovarian hyperstimulation syndrome (OHSS) poses one of the greatest risks to women undergoing assisted reproductive treatments (ARTs, including In Vitro Fertilisation (IVF) and Intra Uterine Insemination (IUI)). OHSS usually occurs in women who have over responded to ovarian stimulation drugs. It is triggered by the effect of Human Chorionic Gonadotropin (hCG) either administered during treatment to trigger the maturation of the oocytes (the eggs) or produced naturally as a result of pregnancy. The ovaries become enlarged and cystic and fluid leaks into various body cavities. Currently, treatment is only usually provided once the condition has progressed to a severe state and the patient requires inpatient treatment. OHSS can be classed as mild, moderate, severe or critical. Moderate cases involve the build-up of fluid in the abdomen (called ascites), increased ovarian size, and abdominal pain. In severe cases, fluid retention and dehydration can lead to changes to the constitution of the blood (haemoconcentration and hypoalbuminemia); in critical cases, further fluid retention can lead to respiratory distress, thrombosis, disturbed renal and liver functions, and death [1].

OHSS can be further clinically classed into early and late. STOP-OHSS trial definitions are based on the Royal College of Obstetricians and Gynaecologists Greentop Guidance on the management of OHSS [2]. Early OHSS is caused by the ovarian stimulation drugs given during ARTs and occurs usually up to 8 days of the final trigger drug (hCG) being given and before embryo transfer has taken place. Late OHSS usually occurs more than 9 or more days after the trigger drug is given and/or if it occurs after embryo transplantation and they are potentially pregnant.

OHSS can be classified into different levels of severity. STOP-OHSS trial definitions (again based on the Royal College of Gynaecologists Guidance) are currently that mild OHSS involves abdominal bloating, mild abdominal pain and an ovarian size of below 8cm. Mild forms of OHSS are fairly common affecting approximately 1:3 women undergoing IVF treatment. Moderate and severe OHSS, although less common (up to 8% for moderate and severe OHSS combined)[2], can have a significant impact on a woman's health resulting in prolonged hospitalisation and posing a significant economic burden on both patient and NHS resources. Moderate OHSS do not meet the criteria of severe and can be defined as having: moderate abdominal pain; fluid accumulation in the abdomen (ascites), confirmed by ultrasound scan and increased ovarian size (8-12cm). Moderate patients may also have nausea with or without vomiting. Patients with severe OHSS would have clinically detectable fluid (clinical ascites) and one of the other features: low urine output, ovarian size of above 12cm, or a haematocrit level above 0.45. Critical OHSS can be distinguished by patients having clinical ascites with one of the following features: large hydrothorax, haematocrit level above 0.55, white cell count of over 25000/ml, very little or no urine, thromboembolism or acute respiratory distress syndrome.

## The STOP-OHSS Clinical Trials

The STOP-OHSS clinical trials plan to test whether earlier active outpatient management interventions for women with moderate to severe, early or late OHSS are acceptable and feasible, and what is the clinical and cost-effectiveness of such interventions compared to conventional conservative

# Sheffield Teaching Hospitals NHS

management. Specifically, in the later OHSS patients, early signals of clinical efficacy and costeffectiveness will be explored. Evidence [3–10] indicates that earlier active outpatient management may help treat OHSS when compared to current management which is conservative and typically involves monitoring the patient until the condition becomes severe and admitting them [2]. We will run two trials – the first is definitive within the early OHSS population ("Early OHSS Trial"), the second is exploratory within the late OHSS population ("Late OHSS Trial"). The inclusion and exclusion criteria for the future trials are in development.

## The need for a review of patient notes

With over 68,000 IVF cycles performed in the UK in 2016 alone, resulting in potentially over 5000 women suffering from severe OHSS, the burden of the problem becomes evident [2]. However, accurate numbers of women suffering from OHSS are not available. In a parliamentary debate, it was noted that a recent investigation by the Press showed that in 2015 there were 836 emergency hospital admissions for severe OHSS despite the HFEA database recording only 60 cases in that period [11]. OHSS may be under-reported as a result of women being admitted to units other than those where they had their fertility treatment. This could result in the loss of follow up data. There is also a paucity of data relating to hospitalisation rates within 28 days which is the primary outcome for the future trials. Due to the lack of accurate data on incidence and hospitalisation, the initial estimates made to calculate the sample sizes needed for the planned RCTs and to understand the statistical behaviour of the designs, and to decide how many sites would be needed to recruit these numbers, and whether the trials are feasible may be unreliable.

Data gathered from sites during the application phase on incidence of moderate and severe OHSS and hospitalisation need to be confirmed with a more thorough investigation of patient notes. We need to confirm that the trials are feasible and sample size assumptions used are reliable, designs are appropriate to address research questions under those reliable assumptions, and patient throughput will be sufficient to recruit the required sample sizes. If, after the review of patient notes, the estimate of the incidence of moderate and severe OHSS or hospitalisation rate within 28 days are significantly changed, an amendment may be needed to the number of centres or recruitment period (either increased or decreased) and study design – or alternatively, the trials may be deemed infeasible.

Gathering information about usual care protocols and practice will contribute towards a consensusbuilding process within Phase 1 of the trial to agree upon the treatment protocols to be used in the trial. The data will also be used to understand whether sites are already giving the proposed interventions as part of their usual care, in order to inform discussions around site set-up. We also collect usual care data to understand variation in usual care across sites which is key in interpreting future results from both trials.

## 2. Aim and objectives

Aim

To conduct a robust review of patient records at our collaborating centres to inform the design of the STOP-OHSS clinical trials and to assess feasibility of conducting these trials.

#### **Objectives**

To contribute to Phase 1 of the STOP-OHSS study by:

- 1. Describing usual care across participating fertility units and assessing variability
- 2. Validating planned study design parameters for both RCTs, specifically by:
  - a. determining the incidence of moderate/severe and early/late OHSS cases who would be eligible for the RCTs

b. determining hospitalisation rates of those patients identified in (a).

## 3. Methods

Data will be collected in two ways:

- a) By requesting usual care protocols (SOPs) via email, and
- b) By requesting completion of an excel database with information about potential cases of moderate and severe OHSS that occurred over a one-year period between 1 March 2019 and 29 Feb 2020, a period prior to the Covid-19 outbreak in the UK.

In order to complete (b) above, sites will be asked to conduct searches in their local databases (such as IDEAS Fertility Clinic Software) that will help them to identify patients that may have experienced moderate or severe OHSS (see data entry guide for search information). Sites will be asked not to search based on hospital admission, as this may lead to overestimation of the true hospitalisation rate. Centres will be asked to record the searches they used to locate the patients and to enter *all* patients returned as a result of these searches in the database.

The database will collect information about the patient's IVF cycle, symptoms of OHSS, diagnosis, blood test results, out-patient treatment and hospital admission. It is designed to understand the patient's trajectory and development of symptoms, and to collect information relating to the trial's inclusion and exclusion criteria. Further design aspects include that most options are drop-down multi-choice options to standardise answers and there are comments boxes to provide further information. Sites are asked to label anyone who has undergone more than one cycle in that year with a specific labelling format to make this clear.

Sites are given a guidance document and training films and asked to complete and return the database to the Trial Manager at Sheffield CTRU.

A Master database will summarise returned data across all sites.

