## 5. Analysis

On receiving back the data from the sites, we will first conduct quality control to view the data and the search history and go back to sites with any questions about missing data or unclear answers.

We will use the data provided by the sites to calculate incidences of moderate and severe OHSS per year, the number of potentially eligible patients in the early and late OHSS population per year, and the proportion of eligible patients that were hospitalised within 28 days with uncertainty (e.g. 95% confidence interval estimated via Wilson score method[12] ref). Descriptive statistical analysis will be used to analyse the data.

SOPs will be analysed using NVIVO or a similar programme and data presented both statistically and textually. Usual care pathways used will be categorised and summarised, presenting information including the number and proportion of sites giving early outpatient management as part of usual care, and contextual information of interest to the trial, including definitions of OHSS types, resolution of symptoms, criteria for hospitalisation.

A detailed quality assurance and data analysis plan has been produced separately to further outline processes.

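### Cases and 28-day admissions come from sites' local databases, with no step shown for learning of admissions elsewhere, although the protocol names these as a cause of under-reporting

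*Protocol*

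**What the plan says.** Protocol, *The need for a review of patient notes*, gives the reason for the review: "OHSS may be under-reported as a result of women being admitted to units other than those where they had their fertility treatment". It adds: "This could result in the loss of follow up data". It also reports that "in 2015 there were 836 emergency hospital admissions for severe OHSS despite the HFEA database recording only 60 cases in that period".

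Protocol section 3 (Methods) has sites search their own local databases, with one fertility software package as the example, and enter every patient the searches return. One restriction applies: "Sites will be asked not to search based on hospital admission, as this may lead to overestimation of the true hospitalisation rate". For each case found, the fields include "blood test results, out-patient treatment and hospital admission".

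Protocol section 5 (Analysis) uses these returns for the yearly incidence of moderate and severe OHSS, the number potentially eligible, and "the proportion of eligible patients that were hospitalised within 28 days with uncertainty", with a Wilson 95% interval as the example. The stated quality control is to look at the data and search history and send queries back to the sites.

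Section 3 refers to a data entry guide, and section 5 to a separate quality assurance and data analysis plan. Neither is shown.

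**The concern.** The protocol names a route by which information is lost, namely admission outside the fertility unit. It then draws both cases and outcomes from a source open to the same loss. A query to a site cannot recover an admission that the site's records never held.

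There are two separate consequences.

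- **28-day rate.** If a woman is found but her admission elsewhere is not in the notes, nothing in the visible text separates not admitted from not known.
- **Incidence.** The reason given for the search restriction concerns only the hospitalisation rate, yet the same list supplies the incidence count. A case traceable locally only through an admission drops out of both.

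The 28-day hospitalisation rate is the planned trials' primary outcome. Together with incidence it may change the number of centres, the recruitment period or the design, or lead to the trials being judged infeasible. The results also go to the STOP/GO assessment (Protocol section 6).

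**Working it through.** The protocol states no expected hospitalisation rate, capture rate or sample size for this review, so there is no figure to reproduce. All rates below are assumptions chosen to show size and direction.

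**Notation**
- h: true 28-day hospitalisation rate (assumed 0.40; 0.20 and 0.60 as a range)
- a: share of admitted cases that the search misses
- b: share of admitted cases that are found but whose admission is not recorded
- c: share of non-admitted cases that the search misses

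**Formulas**
- Share of true cases captured = h(1 − a) + (1 − h)(1 − c)
- Observed rate = h(1 − a − b) / [h(1 − a) + (1 − h)(1 − c)]
- The observed rate is below h exactly when a + b/(1 − h) > c.

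**Step 1. Women already found (a = c = 0).** The observed rate is h(1 − b).

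| b | h = 0.20 | h = 0.40 | h = 0.60 |
|---|---|---|---|
| 0.10 | 0.18 | 0.36 | 0.54 |
| 0.20 | 0.16 | 0.32 | 0.48 |
| 0.30 | 0.14 | 0.28 | 0.42 |

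This error runs one way, and the incidence count is unaffected.

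**Step 2. Does the interval show it?** Take 200 cases (assumed), h = 0.40 and b = 0.30. The review sees 56/200 = 0.28, with a Wilson 95% interval of 0.222 to 0.346. This excludes 0.40. The interval measures sampling error only.

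**Step 3. Cases missed altogether (h = 0.40).**

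| a | b | c | Observed rate | Cases captured |
|---|---|---|---|---|
| 0.1 | 0 | 0 | 0.36/0.96 = 0.375 | 96% |
| 0.3 | 0 | 0 | 0.28/0.88 = 0.318 | 88% |
| 0.3 | 0 | 0.3 | 0.28/0.70 = 0.400 | 70% |
| 0.1 | 0 | 0.3 | 0.36/0.78 = 0.462 | 78% |
| 0.1 | 0 | 0.5 | 0.36/0.66 = 0.545 | 66% |
| 0.2 | 0.1 | 0.3 | 0.28/0.74 = 0.378 | 74% |
| 0.2 | 0.1 | 0.5 | 0.28/0.62 = 0.452 | 62% |

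The captured share never rises above 100%, so missed cases can only lower the count. The rate can come out low, right or high. In these scenarios the direction is the same at h = 0.20 and h = 0.60.

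**Step 4. What an unknown category would give.** Let u be the share of women with unknown admission status, and let 40% of those known be admitted. The bounds are 0.40(1 − u) with no unknowns admitted, and 0.40(1 − u) + u with all of them admitted.
- u = 0.10: 0.36 to 0.46
- u = 0.20: 0.32 to 0.52

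**The case against.** **The restriction is sound.** Searching on admission selects on the outcome and inflates the proportion. This stands for the hospitalisation denominator. Nor does the restriction cause outside admissions to go unrecorded for women already found. What remains is narrower: the stated reason does not cover the incidence count, which uses the same list.

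**The relevant count is of recruitable women.** The incidence objective (Protocol section 2, objective 2a) concerns cases who would be eligible for the trials. A woman visible only through an admission may not have been recruitable for earlier outpatient management. This stands in part, and is why eligible women on any supplementary list need separate reporting.

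**The unseen documents may deal with it.** The data entry guide may already offer an unknown code, and local databases might include a host hospital's records. Both are possible. The protocol nowhere says that an absent record is coded as no admission. However, the protocol itself fixes the data source and the search rule, and neither answers the problem it raises.

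**Stronger readings that the documents do not support.**
- A reader might infer that incidence and the 28-day rate are both certain to be understated. The protocol speaks only of what may or could happen, and Step 3 shows that the rate can also be overstated.
- A reader might divide 60 by 836 and conclude that clinic records capture about 7% of cases. Those figures set a national register against emergency admissions. They signal under-recording but do not measure what patient notes hold.
- A reader might want to estimate missed cases from the overlap of two searches. Both searches would use the same databases, so the lists are not independent. An admission list holds no non-admitted women, and neither list finds a woman with no local trace.

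**Conclusion.** The point holds in limited form. The protocol acknowledges admission elsewhere and possible loss of follow-up, but shows no step for learning of such admissions.

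- **Among women already found,** unrecorded outside admissions can only lower the 28-day rate: from 40% to 36%, 32% or 28% if 10%, 20% or 30% are unrecorded. The Wilson interval does not reflect this.
- **Overall,** the bias of the rate has no known direction, because it also depends on how many non-admitted cases are missed.
- **Incidence** is likely understated. How far this matters for trial throughput is uncertain, since some of the missed women may not be recruitable.

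The 40% rate, the loss shares and the 200 cases are assumptions; the documents give none of them. The conclusion also depends on the unseen data entry guide and analysis plan not already containing the coding and bounds proposed below.

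**What to change.** **(a) Admission status.** Record 28-day admission as yes, no or unknown, where no requires a documented contact after the episode. Record whether the admitting unit was the site's own hospital or another. Do not treat the absence of a record as no. Report the rate among women with known status, with two bounds: none of the unknowns admitted and all of them admitted. If the data entry guide already does this, a sentence in Protocol section 5 stating the bounds is enough.

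**(b) Search lists.** Keep the non-admission search as the only list for the hospitalisation rate. Add an admission-based search, flagged by source and used only as a supplementary incidence count, and report separately those who would have been eligible. It will not find women with no local trace, and this should be stated as a limitation.

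**Cost.** One extra drop-down option, one extra query per site and an amendment to the site guidance. The stated range for the rate becomes wider, so the STOP/GO assessment may be less clear-cut, but it would show the uncertainty that unknown admissions leave.

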## 4. Sample

In this case, as the exercise is meant to understand the feasibility of the STOP-OHSS trial, we will ask all centres interested in taking part in the clinical trial to complete this. We estimate that a maximum of 20 centres may complete the review, but would consider other centres completing it if they are interested in the trial or are on our reserve list.

## 5. Analysis

On receiving back the data from the sites, we will first conduct quality control to view the data and the search history and go back to sites with any questions about missing data or unclear answers.

We will use the data provided by the sites to calculate incidences of moderate and severe OHSS per year, the number of potentially eligible patients in the early and late OHSS population per year, and the proportion of eligible patients that were hospitalised within 28 days with uncertainty (e.g. 95% confidence interval estimated via Wilson score method[12] ref). Descriptive statistical analysis will be used to analyse the data.

SOPs will be analysed using NVIVO or a similar programme and data presented both statistically and textually. Usual care pathways used will be categorised and summarised, presenting information including the number and proportion of sites giving early outpatient management as part of usual care, and contextual information of interest to the trial, including definitions of OHSS types, resolution of symptoms, criteria for hospitalisation.

A detailed quality assurance and data analysis plan has been produced separately to further outline processes.

## 6. Anticipated Impact and Dissemination

The findings from this review of patient notes will be fed back to clinicians as part of a consensusfunding process and meeting in order to confirm treatment protocols that will be acceptable to sites. Master spreadsheets and data arising from this study will be presented to the TSC, DMEC and funders as part of a STOP/GO assessment to assess whether the trial should continue in 2021. Usual care pathway data will also be used within the main clinical trial to describe current usual care and enable use to interpret the trial results correctly.

The review will provide reliable data on moderate and severe OHSS including early and late population which could be used for future treatment, research and decision-making. As such, we aim to publish a journal article. The work may also be presented at conferences and within other journal articles.

## STOP-OHSS – A qualitative study to understand the acceptability and feasibility of new earlier active management treatment of Ovarian Hyper-Stimulation Syndrome (OHSS) v1.1 15/06/20

## Aim

To explore the acceptability and feasibility of earlier active outpatient management interventions for women with moderate to severe, early or late ovarian hyper-stimulation syndrome (OHSS)

## **Background**

## What is Ovarian Hyper-Stimulation Syndrome (OHSS)

Ovarian hyper-stimulation syndrome (OHSS) poses one of the greatest risks to women undergoing assisted reproductive treatments (ARTs, including In Vitro Fertilisation (IVF) and Intra Uterine Insemination (IUI)). OHSS usually occurs in women who have over responded to ovarian stimulation drugs and is triggered by the effect of Human Chorionic Gonadotropin (hCG) either administered during the course of treatment to trigger maturation of the oocytes (the eggs) or produced naturally by a resulting pregnancy. The ovaries become enlarged, develop cysts (fluid filled sacs) and fluid leaks into various body cavities.

OHSS can be clinically classified as early and late. Early OHSS is usually caused by the ovarian stimulation drugs given during treatment, and usually occurs within 7 days of the final drug given (called hCG). Late OHSS usually occurs 10 days or more after the administration of hCG and is caused by endogenous hCG of a resulting pregnancy. The late type is usually more difficult to control, runs a longer course and is more severe [1]. Although mild forms of OHSS are fairly common (approximately 1:3 women undergoing IVF treatment), more severe OHSS, although less common (up to 8% for combined moderate and severe OHSS) [2] can have a significant impact on a woman's health resulting in prolonged hospitalisation and posing a significant economic burden on both patient and NHS resources.

With over 68,000 IVF cycles performed in the UK in 2016 alone, resulting in potentially over 5000 women suffering from severe OHSS, the burden of the problem becomes evident [2]. Although the mean hospital stay is approximately 3 days [1], the duration of stay can be much longer [3].

#### Current treatments

Currently, treatment is only usually provided once the condition has progressed to a severe state and the patient may require intensive inpatient treatment. OHSS can be classed as moderate, severe or critical. Moderate cases involve the build-up of fluid in the abdomen (called ascites), increased ovarian size, and abdominal pain. In severe cases, fluid retention and dehydration can lead to changes to the constitution of the blood (haemoconcentration and hypoalbuminemia). In critical cases further fluid retention can lead to respiratory distress, thrombosis, disturbed renal and liver functions, and death [4].

Admission often results in a significant number of laboratory investigations and blood tests performed on a daily basis. Care often involves multi-disciplinary input and occasionally high dependency or intensive care therapy in women with critical OHSS. Furthermore, complications such as venous thromboembolism can have long term health effects that last well beyond the length of the pregnancy. Therefore, the burden on women of being admitted with OHSS for an undetermined period of time cannot be overstated and neither can the burden of investigations and interventions necessary on the NHS.

Currently, clinical practice usually involves monitoring the patient until the condition becomes severe, at which point the patient is most likely to be admitted to hospital, as recommended by the Royal College of Obstetricians and Gynaecologists (RCOG) green top guideline [2]. This in-patient management often includes drainage of ascitic fluid (paracentesis) which can result in a significant improvement of the condition and an improvement in renal blood fluid, urine output and reversal of the haematological abnormalities [5–7] which not only improves symptoms but the overall condition.

